## **Introduction**

Recurrent aphthous stomatitis (RAS) is the most common painful oral mucosal disease. It affects nonkeratinized mucosa in men and women of all ages, races and geographic regions. The prevalence ranges from 0.7–20% in the general population [1]. In children, the prevalence differs according to age, ranging from 1.2–36.2% [2]. Minor RAS is the most common form, which accounts for approximately 70% to 87% of the population with RAS [3,4] and usually has 1 to 5 ulcers at one episode, with a size of less than 1 cm in diameter [5]. For RAS patients, the ulcer pain associated with each episode may severely interfere with eating, speaking, and swallowing.

Although RAS represents a very common oral lesion, its etiology remains unclear. Some studies have showed that several local and systemic factors, such as local trauma, genetic predisposition, immunodeficiency, zinc deficiency and hormonal changes may play a role in the pathogenesis of RAS. Suspected microbiota may also associate with RAS [6-8]. Since the etiology is unknown, no curative therapy has been described to date. All current systemic or topical treatment methods are to relieve symptoms and accelerate healing. Most systemic medications, although effective, have side effects that limit their general use. Therefore, topical agents remain the first choice for the treatment of RAS, due to their effectiveness and safety.

The application of host-modulating bacteria for therapeutic purposes is one of the strongest emerging fields. Probiotics are live microorganisms, which, when administered in an adequate amount, confer a health benefit on the host [9, 10]. Majority of probiotic bacteria belong to the genera, *Lactobacilli*, *Bifidobacterium*, *Propionibacterium* and *Streptococcus*. Lactobacilli play an important role in the maintenance of health by stimulating the innate immunity as well as by contributing to the balance of the microflora [11].

Probiotics have been documented to exert several actions on a wide variety of immune cells shifting it towards the anti-inflammatory pathway [12]. Probiotics modulate mucosal immune mechanism by reducing production of pro-inflammatory cytokines through actions on NFκB pathways, increasing production of anti-inflammatory cytokines such as IL-10 and host defense peptides such as b-defensin, enhancing IgA defenses, influencing dendritic cell maturation and stimulating the activity of Treg lymphocytes [13-15]. Additionally, probiotic action could be augmented by using prebiotics such as inulin. This combination is known as symbiotic [15].

According to our understanding to the mechanism of probiotics in modulating the local and systemic inflammatory immune process and previous studies [16], it is feasible to investigate the effects of this therapy on RAS. Hence; it is one of the conditions that immune mechanism is

implicated. To the best of our knowledge, no study has been conducted in pediatric population. The aim of this study is to explore the effectiveness of lozenges containing *Lactobacillus acidophilus* (*L. acidophilus*) and *Bifidobacterium lactis*, plus inulin in the treatment of minor RAS in adult and pediatric RAS patients.

## **Patients and Methods**

### ***Study design***

The study is a randomized, controlled, clinical trial. Study population was recruited among patients referred to the department of Oral Medicine and Periodontology and department of Pediatric Dentistry, Faculty of Dentistry, October 6 University (Egypt) and had a provisional diagnosis of minor RAS. The study protocol and consent form were approved by the Institutional Ethics Committee (IEC)/ 23-2016). After explanation of all aspects of the study, characteristics of the product and the available alternative treatments, a signed consent form was obtained from all patients and parents.

### ***Randomization and treatment groups***

We performed power analysis to calculate minimum number of patients for the study. To achieve a significance level (type 1 error) as 0.05 and power (type 2 error) as 0.8, we decided to include 30 patients for each subgroup estimating a dropout rate of 20%. Hence, sixty adult (group A) and 60 children patients (group B) with diagnosis of minor RAS were included in the study. Each group was divided into two subgroups as follows:

Group AI: ChocBalls (*L. acidophilus* containing lozenges, PharmaCare Europe Ltd; [name])

Group AII: (control) Oracure oral gel (15 gm, Amun pharmaceutical company, Egypt)

Group BI: ChocBalls (*L. acidophilus* containing lozenges, PharmaCare Europe Ltd; [name])

Group BII: (control) Oracure oral gel (15 gm, Amun pharmaceutical company, Egypt)

The inclusion criteria for group A is as follows: 1. Males and females aged 18–45 years old, 2. Patients presenting with RAS with the following characteristics: a. Minor aphthous ulcers less than 48 hours' duration prior to enrolment, b. Size no greater than 10 mm in diameter, c. A history that ulcers normally more than 5 days to resolve without treatment. The inclusion criteria for group B is the same except age, children with RAS aged between 3 and 12 years were recruited for the study. The exclusion criteria are as follows: A known history of hypersensitivities, immunologic or systemic diseases, pregnancy, smoking, treatment with systemic steroid or other immunomodulatory agents within 1 month before the study, use of nonsteroidal anti-inflammatory drugs or oral antihistamines within 1 month prior to the study, treatment of the ulcer with any preparation or medication within 72 hours prior to the study, treatment with systemic antibiotics within 2 weeks prior to the study and a history of

adverse reactions to lactose or fermented milk products. Children with a positive family history of RAS were excluded. The nutritional status of the children was evaluated.

After taking a detailed history and clinical examination, all patients eligible for study participation was assigned to the test subgroups (*L. acidophilus* containing lozenges, PharmaCare Europe Ltd; [name]) or control subgroups by using a computer-generated random number list (30 patients for each subgroup). Adult lozenge was composed of the following: *L. acidophilus* 1.5 billion cfu, *Bifidobacterium lactis* 1.5 billion cfu and inulin 0.13 g per lozenge. For children, lozenge was composed of the following: *L. acidophilus* 0.5 billion cfu, *Bifidobacterium lactis* 0.5 billion cfu and inulin 0.13 g per lozenge.

Patients were instructed to melt the *L. acidophilus* containing lozenges in the mouth slowly twice daily for 5 days (day 1 to day 5). The baseline parameters were taken and recorded on the day of the first visit. Effectiveness evaluations were made on the morning of day 3 visit and day 5 visit.

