### ***Clinical outcome variables:***

The index ulcer's size was measured by using a methodology described by Liu et al [17] on treatment days 0, 3 and 5. The investigators measured the maximum and minimum diameters when the ulcer has an oval shape, using a calibrated dental probe with millimeter markings. The two measurements were then be multiplied to represent the cross-sectional areas of the ulcer.

To evaluate pain, a visual analog scale (VAS) consisting of a 10-cm horizontal line between poles connoting no pain (origin) to unbearable pain was used. Subjects was told to mark the line with a vertical line at the point that best represented the present pain level of the ulcer.

The effectiveness indices (EI) of the ulcer size and pain improvement were calculated with the following formula: (V3 and V5 referring to the values measured at Day 3 visit and Day 5 visit, while V1 referring to the baseline value measured before the study entry):  $EI = [(V1 - V3 \text{ or } V5) \div V1] \times 100\%$ . The effectiveness indices were evaluated on a 4-rank scale: (1) Heal:  $EI \geq 95\%$ ; (2) Marked improvement:  $EI < 95\%$ , but  $\geq 70\%$ ; (3) Moderate improvement:  $EI < 70\%$ , but  $\geq 30\%$ ; (4) No improvement:  $EI < 30\%$ . Participants were asked to estimate the average duration of episodes during the past 6 months and the potential to reduce the outbreak frequency of RAS within the next 6 months was investigated. All clinical outcome variables are recorded by an investigator masked about the treatment modality that has been used.

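### Effectiveness is graded as a percentage of baseline, but entry sets no minimum ulcer size or pain, so pain EI is undefined at VAS 0 and one probe mark can move a small ulcer up a rank

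*Combined protocol and SAP*

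**What the plan says.** All references are to the combined protocol and SAP.

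- **Entry** (Randomization and treatment groups). The ulcer criteria for adults are a ceiling, "Size no greater than 10 mm in diameter", a recent onset, "Minor aphthous ulcers less than 48 hours' duration prior to enrolment", and a history of slow resolution without treatment. For children, "The inclusion criteria for group B is the same except age". No inclusion or exclusion criterion sets a smallest size or any baseline pain.
- **Size** (Clinical outcome variables). Diameters are measured "using a calibrated dental probe with millimeter markings", and "The two measurements were then be multiplied to represent the cross-sectional areas of the ulcer".
- **Pain** (same section). A 10-cm VAS "between poles connoting no pain (origin) to unbearable pain was used", so zero is a permitted score.
- **Index** (same section). "The effectiveness indices (EI) of the ulcer size and pain improvement were calculated with the following formula": EI = (V1 − V3 or V5) / V1 × 100%, with "V1 referring to the baseline value measured before the study entry". Four ranks follow: *Heal* at 95% or more, *Marked improvement* from 70%, *Moderate improvement* from 30%, and *No improvement* below 30%.
- **Tests** (Statistical Analysis). Wilcoxon signed rank within groups and Mann-Whitney U between groups. The section does not say whether these are applied to EI, to the ranks or to the measured values. It gives no rule for a baseline of zero.

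**The concern.** A ratio to baseline is stable only when the baseline is well away from zero and large relative to the measurement step. The entry criteria secure neither. They limit the large end, where EI behaves well, and leave open the small end, where it does not.

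The four EI ranks are the only effectiveness grading the plan defines. If they carry the between-group result, two things are at stake. A participant without baseline pain cannot be graded for pain, even if pain appears later. And the same measured change earns a different rank depending only on the size or pain at entry, so some recorded improvements may be no more than reading error.

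**Working it through.** **Inputs from the documents:** size ceiling 10 mm, no floor; probe marked in 1 mm; area = product of two diameters; VAS 0 to 10 cm; the EI formula; rank cut-offs 30%, 70% and 95%; 30 patients per subgroup. The plan states no figure on this point that could be reproduced.

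**1. Pain at VAS 0.** With V1 = 0, EI = (0 − V3)/0, a division by zero. The same holds at day 5. None of the four ranks can be assigned.

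**2. Area, one diameter 1 mm lower.** For an ulcer of a × b mm with 1 mm off b:

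EI = [ab − a(b − 1)] / ab = 1/b

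The other diameter cancels, so an oval ulcer behaves according to the diameter that changes (10 × 3 mm gives 33.3%, as 3 × 3 mm does).

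**3. Area, both diameters of a round ulcer 1 mm lower.**

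EI = 1 − [(d − 1)/d]²

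| Baseline d (mm) | One diameter | Rank | Both diameters | Rank |
|---|---|---|---|---|
| 1 | 100% | Heal | 100% | Heal |
| 2 | 50.0% | Moderate | 75.0% | Marked |
| 3 | 33.3% | Moderate | 55.6% | Moderate |
| 4 | 25.0% | None | 43.8% | Moderate |
| 5 | 20.0% | None | 36.0% | Moderate |
| 6 | 16.7% | None | 30.6% | Moderate |
| 7 | 14.3% | None | 26.5% | None |
| 10 | 10.0% | None | 19.0% | None |

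The 30% cut-off therefore lies within one mark for a diameter of 3 mm or less, or for a round ulcer of up to 6 mm if both readings move. The 70% cut-off is reached in this way only at 1 mm (one diameter) or at 2 mm and below (both).

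**4. Low but non-zero pain.** A fall of 0.5 cm gives 0.5/1.0 = 50% (*Moderate*) from 1.0 cm and 0.5/1.5 = 33.3% (*Moderate*) from 1.5 cm. It gives 0.5/2.0 = 25% and 0.5/5.0 = 10% (both *No improvement*) from 2 cm and 5 cm.

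**5. How often reading error alone could do this.** The documents give no reading error, so this rests on assumptions: a round ulcer that does not change, true diameter uniform within 0.5 mm of the nominal size, independent normal reading error with SD 0.3 to 0.5 mm, and rounding to 1 mm. Simulated chance of EI of 30% or more (400,000 draws per case):

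| Nominal size (mm) | SD 0.3 | SD 0.5 |
|---|---|---|
| 2 | 24.1% | 32.8% |
| 3 | 13.8% | 20.9% |
| 4 | 3.3% | 9.3% |
| 6 | 1.5% | 3.4% |
| 10 | 0.0% | 0.1% |

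**6. Participants without a pain EI.** The share with VAS 0 is not given. Each one is 1/30 = 3.3% of a subgroup. If the share were between 0% and 10% (an assumption), 0 to 3 of 30 would have no pain EI.

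**The case against.** The strongest reply has four parts.

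- **The problem may be rare.** The Introduction describes the disease as painful, and patients were referred with it, so VAS 0 at entry may be uncommon. This stands as a limit on frequency, but VAS 0 is not excluded and low non-zero scores are also affected.
- **Raw values remain available.** Area and VAS are recorded as outcomes, and the Statistical Analysis section does not confine the tests to EI. A reader might infer that a pain-free participant is lost from the pain result altogether. The documents do not support that: only the pain EI and its rank are lost. Nor do they say that the raw values are what will be compared, so the gap remains.
- **Allocation is random and the recording investigator is masked.** A reader might infer a bias towards one treatment. None is shown. For an unchanged ulcer, reading error can only raise the rank, because it starts at the lowest, but this applies to both arms.
- **Readings may be finer than 1 mm.** The plan says the probe has millimetre marks, not that readings are rounded, and it refers to a cited method for the measurement. This stands: the results in steps 2 and 3 describe a 1-mm difference in reading, however it arises.

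Two further inferences are tempting and fail. One is that a minimum size at entry, such as 4 mm, would stop one mark changing the rank. It would not: at 4 mm, one mark on both diameters gives 43.8%. Even from 10 × 10 mm, a follow-up of 9 × 8 mm is 28% (*No improvement*) and 8 × 8 mm is 36% (*Moderate*). Any categorised outcome has such edges; a floor only makes crossing them less frequent. The other is that patients with little pain or tiny ulcers cannot show benefit. Only VAS exactly 0 prevents it: VAS 0.5 to 0 cm is an EI of 100%, and a 2 × 2 mm ulcer can score 50, 75 or 100%.

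**Conclusion.** The point holds within these limits. Followed exactly, the EI rule gives no pain result at baseline VAS 0. It also ranks a 1-mm lower reading as at least *Moderate improvement* when the diameter concerned is 3 mm or less, or when both diameters of a round ulcer of up to 6 mm move. These statements follow from the plan's own formula and cut-offs and need no assumption.

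How many participants are affected cannot be determined, because no baseline distribution is given; the simulated error rates depend on the assumed reading error. Extremely negative EI values at low baselines add little: VAS 0.5 to 1.5 cm is −200% and 6.5 to 7.5 cm is −15%, but both rank as *No improvement*, and rank tests limit the pull of extremes.

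The consequence is a noisier and partly undefined effectiveness grading. It is worth correcting because the remedy costs almost nothing.

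**What to change.** In the Statistical Analysis section, state that the between-group comparison at days 3 and 5 uses ulcer area in mm2 and VAS in cm for all randomised participants, taking the baseline value into account. A rank analysis of covariance would do this and stay close to the planned Mann-Whitney test. Report the EI ranks as descriptive, and show by arm the number whose pain EI is undefined because baseline VAS was 0. Do not restrict the EI ranks to participants above some baseline value, as that would again exclude people by baseline.

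Cost: a sentence or two in the plan, and the EI ranks lose prominence. No participant is lost from the comparison because of a zero baseline.

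The document describes recruitment mostly in the past tense, so a change to entry is probably too late. If recruitment is still open, requiring a baseline VAS above 0 would keep pain EI defined, at the cost of possibly a few screen failures. It would not cure the coarse ranks in small ulcers, so the analysis statement is needed either way.

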### ***Clinical outcome variables:***

The index ulcer's size was measured by using a methodology described by Liu et al [17] on treatment days 0, 3 and 5. The investigators measured the maximum and minimum diameters when the ulcer has an oval shape, using a calibrated dental probe with millimeter markings. The two measurements were then be multiplied to represent the cross-sectional areas of the ulcer.

To evaluate pain, a visual analog scale (VAS) consisting of a 10-cm horizontal line between poles connoting no pain (origin) to unbearable pain was used. Subjects was told to mark the line with a vertical line at the point that best represented the present pain level of the ulcer.

The effectiveness indices (EI) of the ulcer size and pain improvement were calculated with the following formula: (V3 and V5 referring to the values measured at Day 3 visit and Day 5 visit, while V1 referring to the baseline value measured before the study entry):  $EI = [(V1 - V3 \text{ or } V5) \div V1] \times 100\%$ . The effectiveness indices were evaluated on a 4-rank scale: (1) Heal:  $EI \geq 95\%$ ; (2) Marked improvement:  $EI < 95\%$ , but  $\geq 70\%$ ; (3) Moderate improvement:  $EI < 70\%$ , but  $\geq 30\%$ ; (4) No improvement:  $EI < 30\%$ . Participants were asked to estimate the average duration of episodes during the past 6 months and the potential to reduce the outbreak frequency of RAS within the next 6 months was investigated. All clinical outcome variables are recorded by an investigator masked about the treatment modality that has been used.

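### Does a top rank called Heal, reached at a 95% reduction without closure of the ulcer, need to be redefined?

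*Combined protocol and SAP*

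**What the plan says.** Under Clinical outcome variables, ulcer size is built from the largest and smallest diameters, read with a millimetre-marked probe: "The two measurements were then be multiplied to represent the cross-sectional areas of the ulcer". The effectiveness index (EI) is the fall from baseline to day 3 or day 5, divided by baseline and expressed as a percentage, "while V1 referring to the baseline value measured before the study entry". The same index is calculated for ulcer size and for pain on the 10 cm visual analogue scale.

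The index is then graded: "The effectiveness indices were evaluated on a 4-rank scale: (1) Heal", which needs an EI of at least 95%, followed by marked improvement (70% to below 95%), moderate improvement (30% to below 70%) and no improvement (below 30%). Nothing in the document adds closure or zero area as a condition for the top rank, and there is no separate healed yes/no outcome.

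Three points in Randomization and treatment groups bear on this. The entry limit is "Size no greater than 10 mm in diameter". Eligible patients must have "A history that ulcers normally more than 5 days to resolve without treatment". On timing, "Effectiveness evaluations were made on the morning of day 3 visit and day 5 visit". The Statistical Analysis section lists a Wilcoxon signed rank test within groups and a Mann-Whitney U test between groups, and nothing else.

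**The concern.** A reader who meets the word Heal expects a closed ulcer. Here the word is attached to a relative reduction, so an ulcer that is visibly open can receive it, and the larger the ulcer at entry, the larger the remnant allowed. Two patients left with the same open area can fall into different ranks solely because they started at different sizes. A patient with a smaller remnant can even be ranked below one with a larger remnant.

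What would be at stake is the meaning of any healing percentage taken from the top rank. The last efficacy visit is day 5, and eligible ulcers normally last longer than that. A Heal percentage at day 5 could therefore be read as resolution ahead of the natural course, which a 95% reduction does not establish.

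**Working it through.** The plan states no figure for this point, so there is none to reproduce. The check applies the plan's own formula.

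**Inputs.** From Clinical outcome variables: Heal if EI ≥ 95%; size V = largest × smallest diameter; millimetre-marked probe. From Randomization and treatment groups: diameter at most 10 mm; 30 patients per subgroup with 20% dropout assumed. The rounding rule is not given in the text, so whole and half millimetres are both tried. Equal diameters are used for simplicity, with one oval case.

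**1. Permitted remnant.** With V1 the baseline area and Vt the area at the visit, EI = (V1 − Vt)/V1 ≥ 0.95 is the same as Vt ≤ 0.05 × V1.

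| Baseline (mm) | V1 (mm²) | Largest area still Heal (mm²) |
|---|---|---|
| 4 × 4 | 16 | 0.8 |
| 5 × 5 | 25 | 1.25 |
| 8 × 8 | 64 | 3.2 |
| 10 × 10 | 100 | 5.0 |

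The maximum, 5.0 mm², corresponds to about √5.0 = 2.24 mm across.

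**2. Same remnant, different rank.**
- 10 × 10 to 2 × 2: 1 − 4/100 = 96%, Heal.
- 10 × 8 to 2 × 2: 1 − 4/80 = 95%, Heal (oval case, exactly on the cut-point).
- 8 × 8 to 2 × 2: 1 − 4/64 = 93.75%, marked improvement.
- 5 × 5 to 1 × 1: 1 − 1/25 = 96%, Heal.
- 4 × 4 to 1 × 1: 1 − 1/16 = 93.75%, marked improvement.

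**3. Reach.** The smallest baseline at which an open remnant can be graded Heal is the remnant divided by 0.05.
- Whole-millimetre readings, remnant 1 × 1: 1/0.05 = 20 mm².
- Half-millimetre readings, remnant 0.5 × 0.5: 0.25/0.05 = 5 mm².
- A 2 × 2 mm remnant: 4/0.05 = 80 mm², close to the 100 mm² ceiling.

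Below 20 mm² with whole-millimetre readings, Heal already requires a reading of zero. With finer readings the remnant allowed there is under 0.05 × 20 = 1 mm².

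**4. Weight of one patient.** If a Heal percentage were reported, one open ulcer in it would count for 1/30 = 3.3 points, or 1/24 = 4.2 points if 30 × 0.8 = 24 remain. The plan specifies no such percentage.

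**5. Effect on the planned tests.** The plan does not say whether its tests use raw area, EI or the four ranks. On raw area or EI the label plays no part. On the ranks, a Mann-Whitney test uses only order and ties, and renaming the top rank alters neither. In all three cases the p-values are the same.

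**6. Pain.** The same rank allows a residual of up to 0.05 × 10 = 0.5 cm from a baseline of 10 cm. Closure has no meaning for pain, so the rank has to serve as the top grade of a scale shared by both outcomes.

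**The case for a change.** The strongest case for a change is that the remedy costs almost nothing: give the top rank a neutral name and add a count of closed ulcers from diameters already recorded. The Introduction presents faster healing as an aim of treatment, so a loose use of the word matters. Nor can the 95% limit be defended as an allowance for probe error, since a fixed probe error would not justify 5.0 mm² for one ulcer and 0.8 mm² for another. Mid-sized ulcers are exposed too, as the 5 × 5 mm example shows.

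The description of the rule stands, and so does the point about probe error. The need for a change does not. The rank is defined openly by its cut-off, so nothing is concealed. Dependence on baseline follows from choosing percentage change, and any cut-point puts near-equal values on opposite sides. The rule is identical in both arms of each randomised comparison, and the plan has a masked investigator record the outcomes, so the definition does not favour either treatment.

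The proposed replacement also has the fault it is meant to cure. Reserving the word healed for a recorded area of 0 mm² relies on a millimetre-marked probe, and a sub-millimetre open ulcer could be read as zero. With the last visit at day 5, there may also be few or no closures to compare.

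**Conclusion.** The observation is accurate but concerns a label, and the plan need not change. An open ulcer can be ranked Heal, with at most 5% of its baseline area and never more than 5 mm² under the entry limit. With whole-millimetre readings this needs a baseline of at least 20 mm². No planned test or between-arm comparison would come out differently under a new name, and the raw areas remain available to anyone who wants to look at closure.

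This rests on two things. The first is that the top rank is not presented as a closure rate; a sensible report avoids that by giving the 95% cut-off with the label, for size and pain alike. The second is that the rounding convention, which the text does not state, affects only how many patients could be involved. That number cannot be calculated, because no distribution of baseline sizes is given, and it may be zero.

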### **Statistical Analysis**

The data was subjected to statistical analysis using:

- a) Wilcoxon signed rank test for intragroup comparison
- b) Mann-Whitney U- test for inter-group comparison

The level of significance was set at the probability value  $p \leq 0.05$ .

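### Usual episode duration is collected from every participant but is not used to adjust the day 3 and day 5 comparisons, so some precision is probably given up

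*Combined protocol and SAP*

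**What the plan says.** Under Clinical outcome variables, the protocol measures ulcer size on days 0, 3 and 5, scores pain on a VAS, and derives an effectiveness index (EI), the percentage fall from baseline. The same section adds: "Participants were asked to estimate the average duration of episodes during the past 6 months". It does not say when this was asked, or that treated episodes were left out.

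Two entry criteria under Randomization and treatment groups also bear on natural course: "Minor aphthous ulcers less than 48 hours' duration prior to enrolment" and "A history that ulcers normally more than 5 days to resolve without treatment". Both are thresholds. The second sets a lower limit on usual duration and no upper limit.

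Allocation is described as assignment to test or "control subgroups by using a computer-generated random number list (30 patients for each subgroup"), with no stratification by either variable. The Statistical Analysis section consists of a Wilcoxon signed rank test within groups, "Mann-Whitney U- test for inter-group comparison", and a significance level. It names no outcome, covariate, stratum or model.

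**The concern.** The ulcers heal without treatment and are assessed at fixed days counted from study entry. How much healing is seen at day 3 or day 5 therefore depends partly on how quickly that patient's ulcers usually resolve. The EI scales for starting size, but two ulcers of equal area and pain can belong to a fast and a slow healer.

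An unadjusted rank test counts that difference between patients as error. With about 24 evaluable patients per arm in each age group, a real difference between lozenge and gel is then somewhat more likely to be missed, although the plan already asks a question that could remove part of the error.

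**Working it through.** **Inputs from the protocol.** Alpha 0.05 and power 0.8 ("To achieve a significance level (type 1 error) as 0.05 and power (type 2 error) as 0.8"; the text labels power as type 2 error), 30 patients per subgroup, 20% dropout.

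**The plan's own figure.** No effect size, SD or primary endpoint is given, so 30 per subgroup cannot be rebuilt. The dropout step is consistent: 30 × 0.8 = 24 evaluable, and 24 / 0.8 = 30. Solving backwards, 24 per arm with a two-sided t-test at 0.05 has 80% power for a difference of 0.826 SD. This is used below only as a nominal anchor.

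**Why duration is plausibly prognostic.** Counting from a day 0 baseline, an ulcer aged 0 to 2 days at entry is 5 to 7 days old at the day 5 visit. For a usual 6-day episode that is 5/6 = 83% to over 100% of its course. For a usual 14-day episode it is 5/14 = 36% to 7/14 = 50%. The 6 and 14 days are assumptions; the protocol says only more than 5 days. If baseline is counted as day 1, ages are 4 to 6 days and the contrast remains.

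**Closed form.** Let r be the correlation of usual duration with the outcome, within arm and after any other covariate. Adjustment multiplies residual variance by 1 − r², so effective n = 24 / (1 − r²) and the standardised difference becomes 0.826 / √(1 − r²).

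| Assumed r | Effective n per arm | Standardised difference | Power |
|---|---|---|---|
| 0 | 24.0 | 0.826 | 80.0% |
| 0.2 | 25.0 | 0.843 | 81.6% |
| 0.3 | 26.4 | 0.866 | 83.6% |
| 0.4 | 28.6 | 0.901 | 86.4% |
| 0.5 | 32.0 | 0.954 | 89.9% |

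The table does not charge for estimating the covariate. With one covariate and 48 patients, the expected variance inflation is about 1 + 1/(48 − 4) = 1.023, and residual degrees of freedom fall from 46 to 45. Power is then 79.1% at r = 0, 80.7% at 0.2, 82.7% at 0.3 and 89.2% at 0.5. Uninformative recall thus costs about one point.

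**Simulation, all inputs assumed.** Natural duration had mean 8.5 days and SD about 2, entry age was uniform over 0 to 2 days, the probe read to 1 mm, treatment shortened healing after entry by 20%, and there were 24 patients per arm. On day 5 EI, rank ANCOVA on baseline area alone had 63–65% power. Adding usual duration gave 66%, 71–72% and 79–81% when recalled duration correlated 0.3, 0.5 and 0.7 with the current ulcer's natural duration. A second simulation gave gains of about 2, 7 and 18 points, and a loss of about 1 point at correlation 0. Type 1 error stayed near 5%.

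**The two correlations differ.** The closed form uses correlation with the outcome; the simulation uses correlation with the ulcer's natural duration. In an approximate rebuild, recall correlations of 0.3 and 0.5 became about 0.20–0.24 and 0.34–0.42 with day 5 EI. Recall of 0.3 therefore belongs near the r = 0.2 row, a gain of only a point or two.

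**The case against.** The Mann-Whitney test is valid under randomisation, and the plan already limits natural-course variation by restriction: minor ulcers only, under 48 hours old, no larger than 10 mm, with a usual course over 5 days. That stands, so this is an improvement in efficiency and not the repair of an error. Restriction is only partial, however, because usual duration has no ceiling.

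Four stronger readings are tempting, and the documents do not support them.

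- *That the duration answer goes unanalysed altogether.* It is listed among the outcome variables, and the Statistical Analysis section names no variable at all, so a simple between-group test of it may be intended. Such a test would still not adjust the day 3 or day 5 comparison.
- *That ulcer age is already available as a covariate.* The entry criterion needs only a yes or no at 48 hours, and nothing says onset time is recorded. In simulation its added value also depended on whether the ulcer is still growing in its first 48 hours, which the documents do not address.
- *That the duration answer is a clean baseline measure of natural healing.* The protocol does not say it was given before allocation, or as a number, or for untreated episodes only.
- *That the simulated gains are this trial's loss.* They rest on inputs absent from the documents, and they were run for day 5 EI, so they say nothing direct about VAS or day 3.

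**Conclusion.** The point holds as a missed, nearly free gain in precision. Usual episode duration is collected and is probably prognostic, and the planned comparison of day 3 and day 5 results does not use it. A reader might infer that the comparison is biased. It is not biased in expectation; chance imbalance in duration is possible with 24 to 30 patients per arm, and adjustment would help there too.

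The size of the loss cannot be derived from the documents. If usual duration correlates 0.3 to 0.5 with the outcome, a nominal 80% power becomes about 84% to 90%, or about 83% to 89% after charging for the covariate. Weak recall gains a point or two, and uninformative recall loses about one. The change is worth making because the downside is small, but it does not affect the validity of the trial.

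**What to change.** In the between-group item of Statistical Analysis, pre-specify the following, separately for adults and children:

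- A rank ANCOVA of each day 3 and day 5 outcome (ulcer area, VAS and the EI derived from each) on arm, with the baseline value and usual episode duration as covariates. A simpler alternative is a van Elteren test stratified by usual duration above or below the age-group median.
- The Mann-Whitney test kept as the unadjusted sensitivity analysis.
- Usual duration used only if it was asked before allocation, with missing answers filled by the age-group median so that no patient is dropped.
- Ulcer age at entry added as a further covariate only if onset time was recorded as a number at the first visit.

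Under Clinical outcome variables, state when the duration question was asked, in what units, and who answered for young children. Recruitment is described in the past tense. If enrolment is complete, only what was recorded before allocation can be used, and the choice should be fixed before the arms are compared.

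The cost is analysis wording and, if recruitment is still open, two numbers on the baseline form. There is no extra patient, visit or procedure. The downside is that both values are recalled: if recall is uninformative, one or two of about 46 residual degrees of freedom per age group are lost for no gain.
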